4.9 Health-Economic Data Collection (US Sites Only)

In order to further quantify resource utilization and health care costs in the study population and to complement data from the medical records, hospitalization and follow-up resource utilization and cost data may be collected and analyzed by an independent core laboratory. Data to be collected may include, but are not limited to, copies of the patients' hospital bills (UB04) and/or itemized hospital bills. The data will be redacted prior to analysis.

The following personal health information from the billing forms may be collected, but not limited to:

- Patient's hospital admission date
- Patient's hospital discharge date
- ICD-10 diagnosis and procedure codes, HCPCS and CPT codes
- Total charges for hospitalizations
- Number and duration of admissions to rehabilitation hospitals, nursing homes and other chronic care facilities
- Self-reported measures of outpatient medical resource utilization including the number of emergency room visits during each follow-up period

4.10 Subject Death

If a patient dies during or after deployment of the Aortix Pump, the Investigator will make every effort to have an autopsy performed to help determine the extent to which the patient's death was related to the device/procedure. The Aortix pump should be returned to Procyron.

All subject deaths which occur in subjects prior to study exit/withdrawal, regardless of causality or study relationship, must be reported to Procyron. Investigator must provide a detailed narrative summary to include as much detail that is known regarding the circumstances surrounding the death. All deaths will be brought to the clinical event committee for adjudication and will be reported using standard mortality classifications.

4.11 Study Termination

The study may be terminated by the Sponsor at any time with suitable written notice to the Principal Investigator, the reviewing EC/IRB, and applicable regulatory agencies. Similarly, the Principal Investigator may withdraw from

the study at any time, provided that written notice to the Sponsor 30 days prior to the date they intend to withdraw is provided. Scheduled follow-up, as described in **Section 4.8**, should continue for all patients who were treated prior to the termination of the study.

4.12 Protocol Deviations

The Principal Investigator must make every effort to follow the protocol, collect all data required and maintain adequate source documentation. The integrity of the study is dependent on the quality of the data collected. Deviations from the protocol will be documented on a Protocol Deviation eCRF and reviewed with the Principal Investigator to ensure compliance.

The investigator must notify Procyrion or its designee and the reviewing EC/IRB of any deviation from the protocol when specific to the protection of the life or physical well-being of a patient in an emergency. Such notice must be given no later than 5 working days after the emergency occurred.

If a pattern of non-compliance is noted, Procyrion or its designee will determine the course of action to take, assess root cause, review relevant protocol procedures and, as applicable, retrain and verify understanding of the issue in question. This will be documented in the Trial Master Files. In the case of repeated or serious non-compliance, Procyrion or its designee reserves the right to disqualify the offending site.

5. Risk/Benefit Analysis

Procyrion has conducted an analysis of the benefits and risks of the Aortix System and procedure. Below is a summary of the potential risks and benefits of this study.

5.1 Potential Benefits

The Aortix Pump has been designed to reduce the load on the heart, improve cardiac hemodynamics, and improve kidney function. While these benefits have been validated in preclinical studies and n=6 acute clinical implants, the benefits have not yet been evaluated in this ADHF patient population or over the course of multiple days. It is possible that the device may benefit the patient by unloading the heart and improving kidney function more rapidly than with standard care and thereby could possibly reduce the hospital length of stay. These potential benefits are not known and will be evaluated in the study. In addition to the potential benefits to patients enrolled in the study, we expect the information gathered will benefit future heart failure patients.

5.2 Potential Risks

The risks associated with trans-femoral interventions and mechanical circulatory support (MCS) are the predominant risks of the study. Most of the risks of the investigational Aortix System procedure are similar to the risks associated with other percutaneous MCS devices. The likelihood of these risks is unknown since the use of MCS in this patient population has not been rigorously studied. These potential risks include, but are not limited to, the following:

- Allergic Reaction or Hypersensitivity
- Aortic Injury (including aortic puncture, tear, dissection or perforation)

- Anemia
- Bleeding (from the access site or due to anticoagulation therapy)
- Bruising at the Access Site
- Death
- Device Failure
- Device Malfunction
- Device Migration or Dislodgment
- Embolism
- Hematoma
- Hemolysis
- Hepatic Injury
- Immune reaction
- Infection
- Insertion Site Hematoma
- Limb Ischemia
- Need for Additional Intervention (Surgical or Non-Surgical)
- Neurological Event
- Nerve Injury
- Pain
- Pump Thrombosis
- Renal Injury
- Sepsis
- Syncope
- Thrombocytopenia
- Thromboembolic Complication
- Thrombotic Vascular Complication
- Vascular Injury (non-Aortic)
- Vascular steal
- Wound Dehiscence

The risks of the investigational Aortix System procedure are similar to the risks listed above; however, the frequency of some may be increased or decreased with the Aortix System procedure or device. For example, the risks of bleeding may be increased by the large diameter Aortix Delivery and Retrieval Systems and the delivery and retrieval procedures, and the risk of infection as compared to the chronic use of IABP or Impella has not yet been established. Other risks, such as hemolysis, may be reduced due to the unique design and fixation of the Aortix Pump.

Given the size of the 18F ID/21F OD Aortix Delivery System and Aortix Retrieval System, potential vascular complications (as listed above) will be carefully monitored. Prior studies of cardiac devices requiring large-bore vascular access have demonstrated higher rates of vascular access complication with increasing size. In the transcatheter aortic valve replacement (TAVR) pivotal trials, major vascular access complications occurred in 5.9%

(Medtronic CoreValve Revalving System – 18F delivery sheath) to 15% (Edwards SAPIEN valve – 22-24F delivery system) of subjects.²⁷ Although the Aortix Pump may be deployed percutaneously by an interventional cardiologist, for this pilot study, the physician may obtain direct vascular access to the femoral artery via cutdown and direct visualization. During vascular access, ultrasound guided placement, micropuncture needles, and microangiography may be considered to ensure proper placement of the guidewire and minimize vascular injury and bleeding.

Upon retrieval of the Aortix Pump, the femoral artery may undergo primary surgical closure. Additionally, at follow-up visits, the femoral artery and descending aorta may be non-invasively imaged to ensure vessel patency and structural integrity.

Vascular imaging, clinical monitoring, and clinical mitigation steps will be used to minimize the occurrence of these risks. The likelihood of these risks is unknown, as this is the first introduction of the investigational Aortix Pump into a human population with a duration of treatment more than 90 minutes. However, bench-top testing and large animal studies have demonstrated that the Aortix Pump can be safely implanted and retrieved after multiple days of use. Simulated use testing has demonstrated acceptable performance of the device under clinical use conditions and/or repeated use.

There may be other, unknown complications that may occur as a result of this procedure. If these or any of the above complications occur, they may lead to repeat or prolonged hospitalization, repeat procedures, emergency surgery, other emergency procedures, or, in rare cases, death. The study doctor and/or the research staff will make every effort to minimize additional risks.

There are also risks associated with the pulmonary artery catheter insertion procedure, which is non-investigational, but required by the study protocol. The most common risks are bruising at the site of the PAC insertion, excessive bleeding and vein injury or tear. Pneumothorax can also occur as a result of a puncture to the lung. This is more common when the catheter is inserted into the neck or chest veins.

The Sponsor has designed the device to be inherently safe. Failure modes due to the user, the device, or the software were studied and risks were mitigated through safe design, provision of information to the user, or protective measures in the medical device itself, software, or in the manufacturing process. The Aortix System is within acceptable risk levels as determined by the risk analysis conducted on potential hazard use, design, and software conditions.

5.3 Risk Mitigation

In addition, this protocol provides steps to mitigate risk to study patients. These include the following:

- Limited Study Size: A limited number of patients will receive the Aortix Pump in this study to determine performance and safety.
- Treatment Duration: The Aortix Pump will only remain implanted up to the point the investigator determines therapeutic goals have been reached. Alternatively, if the investigator determines Aortix Pump therapy is ineffective or unsafe, Aortix Pump may be retrieved at any time.
- Follow-up Assessments: Patients will be monitored closely for device performance, effectiveness, and adverse events.
- Investigator Selection: The investigators in this study are selected based on their experience in performing large bore cardiovascular interventional procedures and experience treating patients with ADHF with worsening renal function.
- Site Selection: Study sites will have sufficient expertise and resources to manage adverse events and provide appropriate alternative therapies if needed.
- Investigator Training: Investigator(s) will be trained in proper device operation prior to study start. Training will include didactic and hands-on training with the Aortix System.
- Subject Screening: The study protocol includes appropriate precautions in patient selection. For example, patients with known anatomic incompatibilities, significant co-morbidities or uncontrolled cardiovascular or other disease will be excluded.
- Adverse Event Monitoring: Timely detection, treatment, and reporting of all adverse events.
- Adverse Event Monitoring: Enrollment pause based on occurrence of procedural related death or serious procedural related adverse events (see Section 6).
- Independent Safety Monitoring. Use of an external clinical events committee for safety monitoring with timely adjudication of adverse events.

6. Adverse Events

Adverse event definitions used in the study are based on ISO 14155:2011 (Clinical Investigation of Medical Devices for Human Subjects – Good Clinical Practice) as defined below. Specific definitions of key Adverse Events are listed in **Appendix C: Key Adverse Event Definitions**. The Clinical Event Committee may elect to further modify or add to the definitions.

For this clinical study, adverse events will be collected post informed consent when invasive or non-standard-of-care screening begins (i.e. imaging or invasive hemodynamics). For safety reporting, all adverse events will be reported until the patient exits the study. Any unresolved procedural or device related adverse events that are still ongoing past study exit will be reported as being unresolved or unresolvable.

Enrollment will pause if any of the following serious, procedure related adverse events occur:

- Death (Aortix procedure related only)
- Aortic Injury Requiring Surgical Intervention to Repair (Aortix procedure related only)

Enrollment will be paused until the event can be evaluated and discussed with regulatory agencies if appropriate and approval is granted to continue enrollment.

For purposes of this study, minor clinical changes which would normally occur for this patient during the course of having heart failure which are not related to the device, the procedure or the therapy, need not be reported. Examples include but are not limited to ongoing poor appetite, weakness or fatigue. Investigator discretion is expected. If unsure, report as an adverse event.

It is anticipated that due to underlying baseline conditions, all laboratory values may not remain in the range of normal for a given participant. Investigator discretion is required to determine if a laboratory value that remains out of range is associated with an untoward clinical finding that should be reported as an adverse event.

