4.2 Enrollment

The patient is considered enrolled in the study when they sign the informed consent and before imaging screening is initiated. Following Informed Consent, imaging of ilio-femoral and aortic anatomy will be obtained to verify appropriate diameter and evaluate for any abnormalities that would preclude device placement. Imaging modality is up to the site, but one or more of the following modalities are recommended: non-contrast CT, intravascular ultrasound (IVUS) or external arterial ultrasound. Magnetic Resonance Angiography (without contrast) or CO2 angiography may also be considered.^x

If not done previously, PAC placement can occur any time after informed consent is signed and before device placement to confirm inclusion criterion for objective measure of congestion. Alternatively, PAC placement can occur in the cath lab before the Aortix device implant procedure.

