After signing informed consent, a urinary collection device will be placed, if not already present. A Foley catheter is recommended, but an external urine collection device may be used per institution requirements. The urine collection device will be placed (do not measure the urine collected during catheter placement) at least twelve (12 hours) before the Aortix Pump placement. If a urinary collection device is already in place, urine should be discarded. Output and intake should be strictly observed starting twelve hours prior to the scheduled implant. The urine collection device and the strict ins/outs monitoring will continue until the Aortix pump is retrieved. The first measurement of intake and output should occur at least six hours prior to Aortix placement and should be recorded every two hours until the pump is turned on. Measurements will occur at the frequency outlined in **Appendix A**.

Fluid ins should be monitored (IV and Oral) for the entire duration the urine collection device is in place with final measurements taken at the time of device retrieval.

Patients will receive standard medical therapy throughout the study. Patients should be on optimized medical therapy prior to being considered for Aortix Pump placement. To characterize the effect of the experimental device, physicians should not adjust the diuretic or inotrope dosing regimen during the twelve (12) hours prior to or the twelve (12) hours after Aortix Pump placement, unless medically necessary. **Diuretics and inotropes should not be adjusted for twelve (12) hours after the Aortix pump is turned on, however, after that point, while the Aortix pump is running, cessation of medications or down titration of diuretics, inotropes or other medications are allowed.** Adjustments of medical therapy can otherwise be made at any point during the study period at the discretion of the treating physician. All medications and medications adjustments will be captured on eCRFs.

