6.1 Event Reporting Requirements

Adverse events should be reported to Procyrion on the appropriate eCRF using one CRF per AE.

The Investigator must report SAEs and SAEs to Procyrion as soon as possible, but in no circumstances later than 24 working hours after the Investigator first learns of the event, at the following email address:

By email to: [contact]

The initial report must be followed by as much information is available and ideally should include complete documentation, including the time and date of onset, description of the event, severity, duration, actions taken and outcome (if known).

All AEs (regardless of severity or relationship to the study device) will be recorded on the eCRF.

Table 1: Timeline for Reporting of Adverse Events

Type	Report to	Reporting Timeframe (from time of learning of event)
Device Deficiency	Sponsor	Within 2 working days
AE / ADE	Sponsor	Within 2 working days
	EC/IRB	Per EC/IRB reporting requirements
SAE / SADE / USADE / UADE	Sponsor	Within 1 working day
	EC/IRB	Per EC/IRB reporting requirements

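### The protocol's only safety pause stops enrollment, defined as signing consent, so as written it does not cover implants in patients who have already consented

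*Protocol*

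**What the plan says.** **The pause.** The opening text of protocol Section 6 states: "Enrollment will pause if any of the following serious, procedure related adverse events occur". Two events follow: death, and aortic injury that needs surgical repair. Each counts only if related to the Aortix procedure. The rule for lifting the pause is: "Enrollment will be paused until the event can be evaluated and discussed with regulatory agencies if appropriate and approval is granted to continue enrollment". Both sentences act on enrollment. Neither mentions implants, who declares the pause, when it starts, or whose approval ends it.

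**The pause as a mitigation.** Protocol Section 5.3 lists an enrollment pause among the measures that protect patients and refers to Section 6. It describes the trigger more broadly, as procedural death or serious procedural events in general.

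**What enrollment means.** Protocol Section 4.2: "The patient is considered enrolled in the study when they sign the informed consent and before imaging screening is initiated". SAP Section 6.1.1 agrees: the All Enrolled population is everyone who signed the consent form.

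**What lies between consent and implant.** Anatomy imaging and, if not already done, the PA catheter follow consent (Sections 4.2 and 4.4.1). Under Section 4.3 a urine collection device, if none is present, is placed after consent and "at least twelve (12 hours) before the Aortix Pump placement".

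**Reporting.** Section 6.1 requires serious events to reach the sponsor as soon as possible and "in no circumstances later than 24 working hours after the Investigator first learns of the event". Table 1 gives "Within 1 working day" for the same report, and 2 working days for non-serious events.

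**The concern.** Both triggers arise from the procedure, and a patient meets that hazard at implant, not at consent. A pause meant to prevent another exposure before the event has been evaluated should therefore act on implants. This one acts on consent. At any site, a patient who signed before the trigger is already enrolled, so a rule that pauses enrollment does not reach that patient.

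The stake is a further exposure to an unevaluated and possibly fatal procedural hazard. Section 5.2 says that the likelihood of the risks is unknown, because this is the first human use of the pump for more than 90 minutes.

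The reporting wording is a separate and smaller matter. If the two limits for the same report differ, sites do not know which one binds them.

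**Working it through.** The main point rests on wording. The plan gives no figure for it, so there is none to reproduce.

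**1. Can enrollment be read as implant?** The protocol keeps the two apart:
- Section 3.4 enrolls up to 60 patients in order to treat 30.
- The footnote to the platelet exclusion in Section 3.4.2 separates the count at enrollment from the count at the procedure.
- Section 4.8 sets a separate follow-up for enrolled patients with no attempted implant.

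The wider reading would conflict with the protocol's own use of the word.

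**2. Does another rule hold implants?**
- Section 4.11: the sponsor may terminate the study. This is discretionary.
- Section 3.6: the investigator may withdraw a patient. This is discretionary.
- Section 8.1: new information that bears on willingness to continue is discussed with the patient.
- Section 8.4: the sponsor passes new risk information to sites, evaluates adverse events and controls the devices.
- Section 6.3: the events committee meets at least twice a year and has no stated role in the pause.

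None of these is an implant hold.

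**3. How many patients are affected?** Inputs from the documents are 30 implants (protocol Section 7) and 12–24 months of enrollment (Section 3.5). Three assumptions are added: even accrual, a trigger at a random moment, and a time d from consent to implant, which the documents do not give. The calculation uses implants directly, so the differing non-implant estimates (33% in protocol Section 7, 50% in SAP Section 2.3) do not enter.

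Implant rate per day, at 30.44 days a month:
- over 24 months: 30 / (24 × 30.44) = 0.0411
- over 12 months: 30 / (12 × 30.44) = 0.0821

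Expected number consented and awaiting an implant = rate × d. Chance of at least one (Poisson) = 1 − exp(−rate × d).

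| d (days, assumed) | Expected, 24 months | Expected, 12 months | Chance, 24 months | Chance, 12 months |
|---|---|---|---|---|
| 0.5 | 0.02 | 0.04 | 2% | 4% |
| 1 | 0.04 | 0.08 | 4% | 8% |
| 3 | 0.12 | 0.25 | 12% | 22% |
| 7 | 0.29 | 0.57 | 25% | 44% |

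The first row corresponds to the 12-hour minimum for urine collection. The working range is 1–3 days.

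**4. Do the reporting limits agree?** The documents do not define a working day. Converting 24 working hours:
- 8-hour day: 24 / 8 = 3 working days, three times the Table 1 limit
- 12-hour day: 24 / 12 = 2 working days
- 24-hour day: 24 / 24 = 1 working day, the same as Table 1

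The limits agree only if a working day is counted as 24 hours.

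**The case against.** The strongest reply is that silence is not permission. Nothing directs a site to implant during a pause, and Sections 8.1 and 8.4 apply directly to a consented patient awaiting implant. A responsible sponsor would probably hold implants anyway. This stands as far as it goes: the gap is in what the rule covers, not in what it orders. It does not remove the point, because a pause listed as a risk mitigation should not depend on discretion.

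A second reply is that few patients are involved and that d is assumed. Both are true.

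A third is that the remedy affects who receives the device. It extends an existing trial-conduct rule to the step that carries the hazard, and it should leave pumps already in place alone.

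A reader might also infer three stronger things about reporting. The documents do not support them.
- **That a contradictory reporting clock starts the pause.** Section 6 ties the pause to the events occurring and never to the report. The two limits are inconsistent or ambiguous, and they conflict outright only if a working day is shorter than 24 hours.
- **That a serious event may be reported later than a non-serious one.** This needs the short-day reading of the text. Table 1 sets 1 working day against 2, and the text also asks for reporting as soon as possible.
- **That reporting delay adds further implants to this gap.** Over 5 calendar days the expectation is 5 × 0.0411 to 5 × 0.0821 = 0.21–0.41 implants. That is a worst case: an 8-hour day, the full limit used, and a weekend. Over 1 calendar day it is 0.04–0.08. Either figure counts implants before the sponsor is told, which widening the pause would not change.

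**Conclusion.** The point holds on scope. The protocol's only pause rule acts on consent, the hazard arises at implant, and patients between the two are not covered. The expected number affected is small: 0.04–0.25 per trigger event, or about a 4–22% chance of at least one. This rests on even accrual of 30 implants over 12–24 months and an assumed 1–3 days from consent to implant. The gap in the text does not depend on those assumptions.

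The rule also leaves open who declares the pause and when it starts, and its triggers differ between Sections 5.3 and 6. The reporting limit in Section 6.1 needs clarifying, but as a separate and lesser matter. The change should be made because it closes a safety gap cheaply, not because many patients are expected to be affected.

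**What to change.** 1. Reconcile protocol Sections 4.2, 5.3 and 6 so that the pause expressly covers new implant procedures as well as new consents, including patients consented but not yet implanted. Leave management of pumps already in place as it is.
2. State who declares the pause and when it starts.
3. Align the general trigger in Section 5.3 with the two events listed in Section 6.
4. Reconcile the text and Table 1 of Section 6.1 to one reporting limit, with its unit defined.

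The cost is a short protocol amendment, which needs ethics committee or IRB approval (Section 8.3) for sites in two countries, and a notice to sites. The downside is that a few consented patients may not be implanted during a pause.

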Unanticipated Serious Adverse Device Effect (USADE) / Unanticipated Adverse Device Effect (UADE): Serious adverse device effect which by its nature, incidence, severity or outcome has not been identified in the current version of the risk analysis report (or protocol or instructions for use)

Note: Anticipated Serious Adverse Device Effect (ASADE) is an effect which by its nature, incidence, severity, or outcome has been identified in the risk analysis report.

AEs or SAEs will also be classified as to their relationship to the Investigational Medical Device or procedure, as follows:

Not Related: The event is due to an underlying or concurrent illness or effect of another device, drug or intervention and is not related to the investigational device or procedure.

Related: The event could be attributed to the use of the investigational device or procedure.

Note: The Clinical Event Committee may further categorize relatedness categories such as likely related and definitely related for better understanding of AEs.

If an AE or SAE is determined to be related to the investigational device or procedure, the expectedness of the event would further be classified as anticipated or unanticipated. Expectedness is based on the current literature and experience documented in the risk analysis report and/or contained in the *Investigational Plan, Investigator's Brochure, Report of Prior Investigations, or Instructions for Use*.

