7.8 Main Study Endpoints

7.8.1 Primary Safety

A Primary Safety analysis will be performed for the As-Treated population to include:

- Percentage of patients with Serious Adverse Events (SAE) defined as the total number of patients with a CEC-classified SAE from the time of enrollment through 30 days post-implant Follow-Up, compared to the total number of patients within the population. Patients with two or more CEC-classified SAE will be counted only once.
- Percentage of patients with Serious Procedure Related Adverse Events (SPRAE) defined as the total number of patients with CEC-classified SPRAE from the time of implant procedure through 30 days post-implant Follow-Up, compared to the total number of patients within the population. Patients with two or more CEC-classified SPRAE will be counted only once. Procedure Related Adverse Events will be defined as any AE related to Aortix Pump Deployment Procedure or Aortix Pump Retrieval Procedure.

Descriptive summaries will be provided for both Percentage of patients with SAE and Percentage of patients with SPRAE for As-Treated population. Corresponding listing will be provided for As-Treated Population.

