7.9 Safety and Additional Data Analysis

7.9.1 Adverse Events (AE)

CEC classification will be used for the analysis of AEs. Additional overall summary and listing for the Investigator's classification of AEs will be provided.

TEAEs will be defined as AEs not present prior to the start of study procedures, or AEs present before study treatment that worsened after implantation. If a partially missing date or time of onset allows the possibility that an AE may be a TEAE it will be presumed to be a TEAE.

AEs will be summarized by subgroup and overall by the number and percentage of patients who experienced at least one AE of any of the following types: any AE, any TEAE, any TEAE Related to Aortix Therapy, any TEAE Related to Aortix Procedure(Aortix Implant Procedure or Aortix Retrieval Procedure), any TEAE Related to Study Required Procedures, any serious TEAEs, any SAE, any SAE Related to Aortix Procedure, any SAE leading to death, any unanticipated adverse device effect.

AEs will be summarized by categories for the ITT population.

TEAEs will be summarized by category and by relationship for the ITT population.

Listings of all AEs will be provided for the All Enrolled population.

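### The study's only automatic enrolment pause is confined to procedure-related events, so on the most natural reading a death attributed to the pump or the therapy would not trigger it

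*Protocol*

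**What the plan says.** Protocol section 5.3 lists, among its risk mitigations, "Enrollment pause based on occurrence of procedural related death or serious procedural related adverse events (see Section 6".

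Protocol section 6 then gives the operative rule. It opens "Enrollment will pause if any of the following serious, procedure related adverse events occur" and lists two items:

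- "Death (Aortix procedure related only"
- "Aortic Injury Requiring Surgical Intervention to Repair (Aortix procedure related only"

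A pause lasts until the event has been evaluated, discussed with regulators where appropriate, and approval to resume has been given.

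The same section excuses sites from reporting minor heart-failure changes "which are not related to the device, the procedure or the therapy, need not be reported", so it names three causes. Section 6.2 has a single relatedness category covering two of them: "Related: The event could be attributed to the use of the investigational device or procedure". The protocol does not define what makes an event related to the Aortix procedure.

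The SAP does. Section 7.8.1 states: "Procedure Related Adverse Events will be defined as any AE related to Aortix Pump Deployment Procedure or Aortix Pump Retrieval Procedure". Section 7.9.1 reports "any TEAE Related to Aortix Therapy" as a category of its own, next to events related to the implant or retrieval procedure.

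**The concern.** The study exposes patients to something new. Earlier human use of the pump averaged 70 minutes (range 47 to 95; protocol section 1.2). Section 5.2 describes this as the first human use lasting more than about 90 minutes and says the likelihood of the risks is unknown. Here the pump is to run for at least two days initially (section 4.5.2.1) and has been tested for seven days of use (section 4.5). The hazards in section 5.2 include pump thrombosis, embolism, hemolysis, migration and vascular steal, all of which can arise while the pump runs.

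If such an event killed a patient and was attributed to the device or the therapy rather than to deployment or retrieval, nothing in the protocol would require enrolment to stop while the death was examined. Further patients could be implanted in the meantime. A lesser concern is that someone who reads only section 5.3 would think that any serious procedure-related event leads to a pause.

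**Working it through.** The protocol states no figure on this point, so the check is a comparison of texts, followed by a calculation for scale.

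**Step 1. Section 5.3 against section 6.**

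| Event | 5.3 summary | Section 6 list |
|---|---|---|
| Procedure-related death | covered | covered |
| Procedure-related aortic injury repaired surgically | covered | covered |
| Other serious procedure-related event, e.g. limb ischemia or life-threatening access bleeding | covered by its wording | not listed |
| Death attributed to device or therapy | not covered | not listed |

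The third row is the mismatch between the sections. The fourth row is an omission common to both.

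**Step 2. Does procedure related include the running pump?** Four places point to no:

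- both triggers in section 6 carry the restriction to the procedure only;
- section 6 itself names device, procedure and therapy separately;
- protocol sections 3.3.1 and 3.3.2 have one endpoint for serious procedure-related events and a different one for events related to the delivery system, retrieval system and pump;
- SAP sections 7.8.1 and 7.9.1 define procedure related as deployment or retrieval and count therapy-related events separately.

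One place points the other way: section 6.2 puts device and procedure in one category.

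**Step 3. Does another safeguard supply a pause?**

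- Clinical event committee: adjudicates every death (section 4.10) and is guaranteed to meet only twice a year (section 6.3). No pause is attached.
- Serious-event reporting to the sponsor within one working day (section 6.1, Table 1), and sponsor evaluation of events (section 8.4): no pause is attached.
- Steering committee: reviews data and oversees enrolment (section 8.5), with no event trigger.
- Sponsor termination (section 4.11): discretionary.
- The documents describe no data monitoring board.

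**Step 4. Scale.** The planned number implanted is n = 30 (protocol section 7). The chance of at least one event at per-patient risk p is 1 − (1 − p)^30, and the expected number is 30p. The documents give no rate of device- or therapy-related death, so p is an assumed range:

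| p (assumed) | Expected deaths | P(at least one in 30) |
|---|---|---|
| 1% | 0.3 | 26% |
| 2% | 0.6 | 45% |
| 3% | 0.9 | 60% |
| 5% | 1.5 | 79% |
| 10% | 3.0 | 96% |

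For the third row of Step 1, section 5.2 cites major vascular access complication rates of 5.9% to 15% from trials of other large-bore devices.

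- At 5.9%: 30 × 0.059 = 1.8 expected; 1 − 0.941^30 = 83.9%.
- At 15%: 30 × 0.15 = 4.5 expected; 1 − 0.85^30 = 99.2%.

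These rates come from other devices, and this study accesses the artery twice (deployment and retrieval), so they show scale only. Of such events, only a surgically repaired aortic injury or a resulting death is on the section 6 list.

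**The case against.** The strongest reply has four parts.

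**Section 5.3 is a summary that defers to section 6.** Its two halves, a death and serious events, correspond to the two listed items. This stands. A reader might infer that the protocol makes a commitment in 5.3 and breaks it in 6; the cross-reference does not support that. Section 5.3 is also confined to procedural events, so it never undertook to cover a device-related death. What remains is that 5.3 reads wider than the list.

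**The trigger can be read broadly.** Section 5.2 likens the risks of the Aortix procedure to a list that includes pump thrombosis, embolism and hemolysis, and section 6.2 merges device and procedure. The restriction may have been meant only to exclude deaths from other study procedures, such as pulmonary artery catheterization, and the SAP contains no pause rule of its own. This partly stands: the narrow reading is the more natural one, not the only one. But a safety trigger that two sites could apply differently needs clarifying anyway.

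**Other safeguards exist.** This stands as a limit on the claim. A reader might infer that later patients depend mainly on the pause rule, but nothing in the documents ranks it so, and independent adjudication and rapid reporting are real protections. None of them is an automatic pause.

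**Time on the pump is not the measure.** A reader might infer that, because nearly all pump time falls outside the two procedures, the rule misses nearly all the risk. That does not follow. The trigger turns on attribution, not timing: a death on day 4 from an access injury is procedure related and would pause enrolment. Exposure time is not risk either, and the only complication rates in section 5.2 concern vascular access.

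**Conclusion.** The concern holds in a limited form. Section 6 holds the study's only automatic enrolment pause. On the most natural reading, a death attributed to the device or therapy falls outside it, while multi-day pump operation is the exposure with no earlier human data. Section 5.3 shares that omission and separately reads more broadly than the list it cites.

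The conclusion rests on reading the procedure restriction in line with section 6's own three-way distinction and the SAP definition. It says only that no pause is automatic; the sponsor could still stop enrolment at its discretion. The size cannot be estimated from the documents. The 26% to 96% range depends wholly on the assumed 1% to 10% risk and shows only that the situation is plausible in 30 patients. This should be corrected, and a wording change is enough.

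**What to change.** Amend protocol sections 5.3 and 6 together:

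1. Use one list of pause events, and limit 5.3 to the events that section 6 actually lists.
2. Word the death trigger with the protocol's own relatedness category from section 6.2 (investigational device or procedure), with therapy named explicitly. If device- and therapy-related deaths are left out on purpose, say so and give the reason.
3. Define what counts as related to the Aortix procedure, consistently with SAP section 7.8.1.
4. State who decides relatedness for the trigger. The committee is guaranteed only two meetings a year, so the text should say whether the investigator's or sponsor's initial classification is enough to start the pause.

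Whether other serious procedure-related events belong on the list is for the sponsor and its clinical advisers to decide.

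The cost is a wording amendment and possibly more pauses. Under the assumed risks above, 0.3 to 3 deaths would newly meet the trigger over the study. How long each pause would last cannot be stated in advance, because it depends on evaluation, any discussion with regulators, and approval to resume.
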